3.4. A pilot study demonstrates that AF ablation increases IsoLG adduct levels

In preparation for this trial, a pilot study (IRB #171722) was conducted to demonstrate the feasibility of the study protocol, demonstrate that IsoLG-adduct levels increase following AF ablation, and generate preliminary data for the power/sample size analysis. These measurements are made using a cellular system (since IsoLG adducts are not free in the circulation), and has used IsoLG measurements in monocytes and dendritic cells (DC).³⁰ Over an 8-week period, 11 subjects who met the eligibility criteria for our proposed clinical trial were prospectively enrolled and underwent AF ablation. The data from our pilot study support the following conclusions:

1. The rate of participant enrollment was sufficient to meet the enrollment target of this proposal. We have proposed to enroll 1 participant per week to accrue 162 participants over 36 months. We enrolled 1.375 participants per week in the pilot study.
2. AF ablation resulted in a statistically significant increase in circulating IsoLG-adduct levels. IsoLG-adduct levels were measured in blood samples collected pre-ablation and on post-procedure day #1. IsoLG-adduct levels increased in 82% (9/11) of subjects, and the mean increase was 23% in DCs (Pre: $41 \pm 16\%$ vs. Post: $63 \pm 17\%$; $P=0.02$; **Figure 4, top panel**) and 21% (Pre: $38 \pm 19\%$ vs. Post: $59 \pm 18\%$; $P=0.04$) in monocytes following ablation.
3. There was an early recurrence of AF in 45% of participants (5/11). This demonstrates that, similar to other published reports, early recurrence of AF is common in our study population and is sufficient to power the primary endpoint of Aim 1, which is AF recurrence within 28-days following ablation (**Figure 4, bottom panel**). This is comparable to the early recurrence rate of AF from numerous other published reports, which is $\sim 50\%$.^{21,23}

[figure not shown]

Figure 4: (Top) There is a significant increase in the proportion of dendritic cells containing IsoLG-adducts from pre-ablation to post-operative day #1 (POD1; $P=0.02$). **(Bottom)** 45% of participants had an early recurrence of AF within our proposed 28-day monitoring period.

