10.2. Aim 2 (Biochemical Endpoint)

Primary hypothesis: The primary endpoint for Aim 2 will be the IsoLG-adduct content of dendritic cells expressed as a percentage (IsoLG-adducted dendritic cells/total dendritic cells x 100). We will test the hypothesis that 2-HOBA reduces the change in IsoLG-adduct levels that occurs with AF ablation (as measured on post-procedure day #1 minus pre-ablation blood samples).

Sample size and power (Aim 2): Our pilot data shows that the change in dendritic cell IsoLG-adduct level is 23% following ablation in our placebo (control) group and we expect the range of possible observed reduction to be 20-40%. With n=81 participants in each arm, the study provides at least 80% power to detect a minimal 22% reduction in IsoLG-adduct level at two-sided significance level of 5%.

Primary Analysis (Aim 2): Our primary analysis will use multivariable linear regression to test whether our primary determinant (2-HOBA versus placebo), significantly reduces the change in IsoLG-adduct levels (continuous), adjusted for baseline pre-ablation IsoLG-adduct level and other potential confounding factors: age, sex, method for pulmonary vein isolation (radiofrequency versus cryo), additional ablation lesions (yes/no), and BMI (continuous). The IsoLG content of dendritic cells adjusted for baseline level will be presented for both treatment arms, together with corresponding 95% confidence intervals (CIs) and p-values will be graphically interpreted using boxplots, partial effect plots, residual plots, etc.

Secondary Analysis (Aim 2): A secondary endpoint will be the IsoLG-adduct level in monocytes. Due to the prohibitively labor-intensive process required to measure IsoLG content in dendritic cells and monocytes, only the pre-ablation and post-procedure day#1 samples will be analyzed for the analysis. However, blood samples from 2 additional time points (baseline and post-procedure day #28) will be available for pharmacokinetic

analysis and secondary analysis of other serological markers. These will include malondialdehyde and other biomarkers of oxidative stress.

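### The Aim 2 claim of at least 80% power for a 22% reduction cannot be reproduced from the pilot data; read as 22% of the ablation-related rise, power is about 47–59% under the planned model

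*Combined protocol and SAP*

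**What the plan says.** Section 10.2 defines the Aim 2 endpoint as the percentage of dendritic cells carrying IsoLG adducts, and states the hypothesis as follows: "We will test the hypothesis that 2-HOBA reduces the change in IsoLG-adduct levels that occurs with AF ablation". The change is the post-procedure day 1 value minus the pre-ablation value. The primary analysis is a linear regression of that change, adjusted for the pre-ablation level and other covariates.

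The power paragraph in the same section takes the pilot rise of 23% as the control-arm change, adds that "we expect the range of possible observed reduction to be 20-40" percent, and concludes, for 81 per arm, that "the study provides at least 80% power to detect a minimal 22% reduction in IsoLG-adduct level at two-sided significance level of 5" percent. No base for the 22%, no SD, no correlation and no formula is given.

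The only source data are in section 3.4. In 11 patients, "the mean increase was 23% in DCs", from 41 (SD 16) to 63 (SD 17), P=0.02, test not named; 9 of 11 rose. Section 10.1, under the interim analyses, says that Aims 2 and 3 will be regarded as exploratory.

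**The concern.** The hypothesis is about reducing the rise. The power paragraph starts from the rise, gives an expected range of reduction, and then gives the 22%. Read in that order, the 22% is a fraction of a 23-point rise, about 5 points, which is small against pilot SDs of 16 and 17. A two-arm comparison with 81 per arm would not be expected to reach 80% power for it.

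Aim 2 is a Specific Aim with its own primary endpoint and a formal power statement. If that statement does not hold for the effect the sponsor expects, anyone who later weighs a null biochemical result will credit the comparison with more sensitivity than it has.

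**Working it through.** **Inputs.** n = 81 per arm, two-sided 5% (section 10.2). Pre 41 (SD 16), post 63 (SD 17), rise 23, P=0.02, n = 11 (section 3.4; the rounded means differ by 22, but the stated rise is 23). The pre/post correlation r is not in the documents; 0 to 0.5 is assumed below.

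**Formulas.** Power ≈ Φ(δ / (SD × √(2/81)) − 1.96), with √(2/81) = 0.157. The noncentral t agrees within 0.5 percentage points. Residual SD after adjustment for the pre-ablation value = 17 × √(1 − r²). Regressing the change or the post value on the pre value gives the same residual. The other covariates are ignored, since the documents give no figures for them.

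**Trying to reproduce the 80%.** For δ = 0.22 × 23 = 5.06, 80% power needs SD = 5.06 / (2.80 × 0.157) ≈ 11.5, or 11.4 with the noncentral t. No such SD is stated. A two-proportion comparison of 63% with 41% at 81 per arm gives 80.6%, but that treats a continuous endpoint as binary and is not described in the plan. It is a possible origin of the figure and no more.

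**Power for 22% of the rise (5.06 points), planned model.**
- r = 0: residual SD 17; 5.06 / (17 × 0.157) = 1.89; power 47%.
- r = 0.5: residual SD 17 × √0.75 = 14.7; 5.06 / (14.7 × 0.157) = 2.19; power 59%.

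**What 80% would require.** 17 × √(1 − r²) = 11.4 gives r ≈ 0.74. The SD of the change would then be √(16² + 17² − 2 × 0.74 × 16 × 17) ≈ 11.9, and a paired t-test on 11 patients would give t = 23 × √11 / 11.9 ≈ 6.4, P below 0.0001. The pilot reports P=0.02.

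**Smallest difference with 80% power.** 2.80 × SD × 0.157 = 7.5 points at SD 17 (33% of 23) and 6.5 points at SD 14.7 (28% of 23).

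**The plan's own 20–40% range, as a share of the rise.** 20% is 4.6 points, power 41–51%; 40% is 9.2 points, power 93–98%.

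**Other bases for the 22%, planned model.**

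| Base | Target, points | Share of 23-point rise | Power, SD 17 to 14.7 | 20–40% range in points |
|---|---|---|---|---|
| Pre level (41) | 9.0 | 39% | 92–97% | 8.2–16.4 |
| Post level (63) | 13.9 | 60% | over 99% | 12.6–25.2 |
| Percentage points | 22 | 96% | over 99% | 20–40 |

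In every row the target exceeds the 6.5–7.5 points detectable with 80% power, so 22% is not the minimal effect. In the last two rows the upper part of the range exceeds the whole rise.

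**The case against.** The strongest reply is that the sentence speaks of a reduction in the adduct level, not in the change. On any level-based or percentage-point reading, at least 80% power is true under the planned model. This stands as arithmetic, so the 47–59% must stay conditional on the base. It does not rescue the paragraph: on those readings 22% is not the smallest detectable effect, and two of the three sit badly with the 20–40% range. The pre-level reading comes closest. An unadjusted change score with r near 0.23 (SD about 20.5) would put 80% power at 9.0 points. But that correlation is not in the documents, the plan does not use an unadjusted analysis, and the hypothesis does not concern the pre-ablation level.

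A reader might infer that power is as low as 21%. That figure follows from an SD of change of 23 × √11 / 2.764 = 27.6, obtained by inverting P=0.02 as a paired t-test, and from an unadjusted change score. The plan adjusts for baseline, and section 3.4 names no test. An SD of 27.6 also implies r = (16² + 17² − 27.6²) / (2 × 16 × 17) ≈ −0.40. Even at that correlation the residual SD is 15.6 and power is 54%. The documents therefore do not support 21% for the planned analysis.

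Nor is 59% a ceiling: r = 0.5 is an assumption, and SDs from 11 patients are imprecise. A 95% interval around 14.7 runs from about 10.3 to 25.8, which corresponds to power of about 87% down to 24%. So 80% power is not excluded; the pilot figures simply do not point to it.

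Finally, Aim 2 is exploratory and the trial is sized on Aim 1. That limits the consequence. The documents do not say that a null Aim 2 result would count against target engagement.

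**Conclusion.** The statement of at least 80% power for a 22% reduction cannot be reproduced from the inputs the plan gives. On the reading that fits the stated hypothesis, the planned analysis has about 47–59% power, and its 80%-power detectable difference is 28–33% of the rise rather than 22%. This rests on the pilot post-ablation SD of 17, on an assumed pre/post correlation of 0 to 0.5, and on the pilot rise carrying over to the trial. The last assumption needs care: the pilot sample was taken on day 1, whereas the visit schedule in section 6.0 lists a draw at the end of ablation and no day 1 draw.

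It would go too far to say that the claim is false on every reading, or that the trial as a whole is underpowered. The first fails on the level-based readings; the second fails because Aim 1 sets the sample size. The point is worth correcting because the power claim is formal and the correction is cheap.

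**What to change.** In section 10.2, state what the 22% is a percentage of, the residual SD, the assumed pre/post correlation (labelled as an assumption, not as pilot data) and the formula. Then restate the figure. If the rise is the intended base, wording such as this would serve:

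*Assuming a pre/post correlation of 0 to 0.5 and the pilot post-ablation SD of 17 points, 81 participants per arm give 80% power at two-sided 5% for a between-arm difference of about 7.5 to 6.5 percentage points (33–28% of the 23-point rise). Power for a reduction of 22% of the rise is about 47–59%. Aim 2 is exploratory.*

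If another base was intended, name it, express the target in points and as a share of the rise, and reconcile it with the 20–40% range. If the sponsor holds the individual pilot data, the observed correlation should be reported next to the assumed range.

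The cost is a change of wording. No extra patients or measurements are needed, but the stated figure becomes less favourable.

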5.0 ENROLLMENT AND RANDOMIZATION

Recruitment and informed consent: Eligible subjects will be identified through EPIC. A member of the study team will request an introduction from the clinical staff. If the patient agrees, a member of the study team will approach the patient in person in Arrhythmia Clinic or by phone prior to AF ablation. Information describing the study, why the research is being done and what will be learned will be provided. The risks as described in this protocol will be delineated. The benefits will be described as general scientific knowledge, along with potential treatment advances. No direct immediate benefit to the subjects is anticipated. Informed consent will be documented with the subject's signature using an IRB-approved consent form for this protocol. An option will be available for phone consent with electronic signature.

Randomization: This will be a double-blind, randomized study. Eligible subjects will be randomized according to a stratified permuted block scheme with a block size of 8. This ensures that the cumulative number of assignments to each treatment (2-HOBA or placebo) will be in balance after each block of assignments had been made. Stratification will be made based on: 1) the planned ablation technique, cyroballoon vs. radiofrequency, 2) paroxysmal vs. persistent atrial fibrillation, 3) *de novo* vs. repeat ablation. A statistician will design the randomization table and enable the randomization tool within REDCap. After a patient enrolls for the study, the study nurse will determine the treatment assignment using the randomization tool in REDCap.

The study drug will be started 3 days prior to ablation. The dose of 2-HOBA will be 750mg three times per day (TID). At least 24 hours in advance, the study nurse will notify IDS to randomize the participant and prepare the study drug. MTI will provide 2-HOBA to the IDS as a 250 mg capsule. MTI will also provide matching

placebo capsules. The study nurse will arrange for the study drug to be given to the participant in-person or mailed. The total duration of the study drug is 31 days (3 days before ablation + 28 days after ablation).

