Primary Analysis (Aim 1): All FAS will be included in the primary analysis of AF recurrence, the primary efficacy endpoint. Binary recurrence of AF will be compared between treatment and control using a chi-square test. The primary analysis will be performed using a multivariable logistic regression model, where the dependent/outcome variable is the early AF recurrence (yes/no) by the end of the 28-day follow-up and the primary independent/predictor variable is the treatment arm (2-HOBA or placebo). Adjustment will be made for age, gender, AF type (paroxysmal versus persistent), method for pulmonary vein isolation (radiofrequency versus cryoablation), additional ablation lesions (yes/no), BMI (continuous), and hours of monitoring (0-672 hours). To avoid over-fitting our multivariable logistic regression model, a 10:1 ratio for degrees of freedom per the less frequent outcome event will be used in our modeling. Nonlinear form of the continuous predictors (age, BMI, and hours of monitoring) will be considered when building the model with restricted cubic splines. Models will be evaluated for goodness-of-fit, and internally validated for the calibration and discrimination performance using the bootstrap method.

Secondary Analysis (Aim 1): A secondary analysis will analyze a surrogate of AF burden as the endpoint and designed to account for the impact of cardioversion on AF burden assessment. AF burden is the percentage of time in AF, atrial tachycardia, or atrial flutter over total time monitored. The secondary analysis will use the data

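### The Aim 2 model omits two of the three randomisation strata and the Aim 1 model omits one, so the analyses only partly reflect the stratified design

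*Combined protocol and SAP*

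**What the plan says.** Section 5.0 uses a "stratified permuted block scheme with a block size of 8". The factors are given as "Stratification will be made based on: 1) the planned ablation technique, cyroballoon vs. radiofrequency", then "paroxysmal vs. persistent atrial fibrillation, 3) *de novo* vs. repeat ablation".

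Section 10.1 (Primary Analysis, Aim 1) specifies a logistic model: "Adjustment will be made for age, gender, AF type (paroxysmal versus persistent"), followed by "method for pulmonary vein isolation (radiofrequency versus cryoablation), additional ablation lesions (yes/no), BMI (continuous), and hours of monitoring (0-672 hours"). Technique and AF type are there; de novo/repeat is not. The unadjusted chi-square comparison in the same paragraph uses no strata.

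Section 10.2 (Primary Analysis, Aim 2) specifies a linear model for the change in dendritic-cell adduct level, adjusted for the pre-ablation level and "age, sex, method for pulmonary vein isolation (radiofrequency versus cryo), additional ablation lesions (yes/no), and BMI (continuous"). Of the three strata, only technique appears.

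The general strategies in Section 10.0 mention the stratification factors only for descriptive baseline summaries. No section adds the missing strata to a model or says why they are left out.

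**The concern.** Stratified blocks balance the arms on factors expected to matter. If a linear model then omits those factors, the variation between strata stays in its residual although the design has largely removed it from the treatment contrast. The reported standard error is then larger than it need be and the test is conservative. What is at stake is precision, not false positives. The two models also disagree: AF type is adjusted for in Aim 1 and dropped in Aim 2 without comment.

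A related detail is that the stratum is the planned technique, while both models refer to the method of pulmonary vein isolation without saying planned. A participant whose technique changed would be modelled in a different category from the one used at randomisation.

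**Working it through.** **1. Strata against model terms**

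| Stratum (Section 5.0) | Aim 1 logistic (10.1) | Aim 2 linear (10.2) |
|---|---|---|
| Planned technique | included, not specified as planned | included, not specified as planned |
| AF type | included | missing |
| De novo/repeat | missing | missing |

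Table 3 in Section 4.0 admits repeat ablation only in persistent AF with planned non-pulmonary-vein ablation. AF type and ablation history therefore have three possible combinations, and with technique there are 3 × 2 = 6 possible strata out of 8 nominal ones.

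**2. The plan's own power figures**

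Aim 1: 81 per arm, 48% versus 29%, one-sided 0.046. The pooled rate is 0.385. The null SE is √(2 × 0.385 × 0.615/81) = 0.0765. The alternative SE is √((0.48 × 0.52 + 0.29 × 0.71)/81) = 0.0750. Power = Φ((0.19 − 1.685 × 0.0765)/0.0750) ≈ 0.79, close to the stated 81%; this point does not dispute it.

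Aim 2: no SD of the change is given, so the 80% cannot be reproduced. On a standardised scale, 80% power at two-sided 5% needs (1.960 + 0.842) × √(2/81) = 0.44 SD. That effect is used below.

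**3. Aim 2: effect of the omission**

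Assumptions, because the documents give none: 50% persistent AF, 30% of those repeat, and an effect of *b* residual SDs for persistent AF and again for repeat. The trial of 162 was simulated with stratified blocks of 8 (15,000 trials per setting), fitting the model without and with the missing strata.

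| *b* | Mean SE, omitted / added | Ratio | Type I error, omitted / added | Power at 0.44 SD, omitted / added |
|---|---|---|---|---|
| 0 | 0.1593 / 0.1596 | 1.00 | 0.049 / 0.048 | 0.786 / 0.784 |
| 0.25 | 0.1608 / 0.1595 | 1.008 | 0.047 / 0.047 | 0.772 / 0.778 |
| 0.5 | 0.1656 / 0.1596 | 1.038 | 0.047 / 0.051 | 0.757 / 0.783 |
| 1.0 | 0.1833 / 0.1595 | 1.149 | 0.035 / 0.050 | 0.665 / 0.779 |

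Rounding the SEs to three decimals first gives 0.6%, 4% and 14%. Bias is about zero throughout. Monte Carlo error on one power figure is about √(0.78 × 0.22/15,000) = 0.003, so the difference at *b* = 0.25 should be read as near zero.

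The excess at *b* = 1.0 has two parts. The actual sampling SD of the estimate (no treatment effect) is 0.171 with the strata omitted and 0.160 with them added, which is a real loss. The model SE of 0.183 then overstates 0.171 by about 7%.

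Closed-form ceiling: the stratum contribution is 0, *b* or 2*b* with probabilities 0.50, 0.35 and 0.15. Its mean is 0.65*b* and its variance (0.35 + 0.15 × 4 − 0.65²)*b*² = 0.5275*b*². If no retained covariate captured any of it, the SE ratio would be √(1 + 0.5275*b*²) = 1.016, 1.064 and 1.236 for *b* = 0.25, 0.5 and 1.0. The simulated ratios are lower, as expected when a retained covariate, notably additional lesions, absorbs part of the stratum effect.

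**4. Aim 1: effect of omitting de novo/repeat**

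The true log-OR is ln[(0.29/0.71)/(0.48/0.52)] = −0.815. There were 8,000 trials per setting, with two-sided 5% tests.

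| Repeat log-OR | Mean SE, omitted / added | Power, omitted / added | Type I error, omitted / added |
|---|---|---|---|
| 0 | 0.351 / 0.353 | 0.694 / 0.697 | 0.055 / 0.055 |
| 0.7 | 0.354 / 0.358 | 0.687 / 0.693 | 0.049 / 0.050 |
| 1.4 | 0.357 / 0.369 | 0.644 / 0.659 | 0.055 / 0.059 |

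Adding the stratum raises the SE. Omitting it pulls the estimate slightly toward zero (−0.83 against −0.88 at log-OR 1.4). The largest power difference is 1.5 points, and there the type I error is also slightly higher with the term added.

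**5. Room in the Aim 1 model**

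Expected events are 81 × 0.48 + 81 × 0.29 = 38.9 + 23.5 ≈ 62, the less frequent outcome. At 10 per degree of freedom that allows 6. The listed model, all terms linear, uses 8: treatment, age, gender, AF type, method, additional lesions, BMI and hours of monitoring. De novo/repeat would be the ninth.

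**The case against.** The strongest reply is that little is lost. Technique is in both models and AF type is in Aim 1. Every eligible repeat case has persistent AF and planned extra lesions, so the additional-lesions term partly stands in for repeat status. Aim 2 is declared exploratory in Section 10.1, its error is on the conservative side, and nothing in the documents shows that AF type or repeat status predicts the change in adduct level. All of this stands, and it limits the size of the point. It does not remove it: de novo patients can also receive additional lesions, and that term describes the procedure, which follows randomisation, so it is not the stratum as randomised.

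Three stronger readings are tempting and are not supported:

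- A reader might infer that the standard errors ignore the design altogether. They reflect it in part.
- A reader might infer that the primary Aim 1 standard error is also too large. In a logistic model the effect runs the other way, as step 4 shows.
- A reader might infer a definite loss of precision because stratification implies prognostic strength. The strata were chosen for the trial as a whole, and their strength for the biochemical endpoint is not documented; zero is within the plausible range.

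**Conclusion.** The omissions are exact: two of three strata in Aim 2 and one of three in Aim 1, without justification. For Aim 2 this is an unbiased, conservative inefficiency. It is negligible for stratum effects up to about 0.25 SD, modest at 0.5 SD (SE about 4% larger, about 2.5 points of power), and material only at about 1 SD (14 to 15%, about 11 points). These sizes rest on the assumed shares of 50% persistent AF and 30% of those repeat, and on effects beyond the listed covariates. For Aim 1 the point is one of consistency with the design; the gain is at most about 1.5 points of power at an assumed repeat log-OR of 1.4. This is an inexpensive improvement, not a threat to the validity of either analysis.

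**What to change.** **Aim 2.** Add the strata as randomised: planned technique, plus one 3-level factor (paroxysmal; persistent de novo; persistent repeat). The listed model has 7 terms including treatment and baseline level. The new factor adds 2 degrees of freedom, making 9 for 162 participants (18 per degree of freedom). When the strata are not prognostic, the simulated cost is 0.2 points of power.

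**Aim 1.** Do not add a ninth term. Give the randomised strata priority within the 10:1 limit: treatment (1), planned technique (1) and the 3-level factor (2) use 4 of about 6 degrees of freedom. Make room by replacing a covariate measured after randomisation, such as additional ablation lesions or hours of monitoring. Adjustment for duration of smartwatch use is already a separate secondary analysis. Replacing one term leaves the count at 8, and removing both leaves 7, so the SAP should also name which remaining covariates are kept to meet the rule, or state why it is relaxed.

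In both models, say that strata are taken from the randomisation record. The cost is SAP wording before unblinding; the data are already held.
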